Participants: A total of 94 current WP smokers (47 low dependent, 47 high dependent) will be recruited from the general community via internet advertisements (i.e., Craigslist, Facebook, and Twitter) as well as flyers and word-of-mouth advertising at local WP bars and lounges in the Oklahoma City Metropolitan Area. Based on our team's previous studies we conservatively assume a 20% attrition rate; thus, we will need to recruit 94 participants to have 76 complete all four sessions. WP smokers will contact a study representative and be screened over the telephone or self-screened online via computer based questionnaire. Consistent with other laboratory studies of waterpipe smoking,^{21,28,30,32,55,63,64} participants who meet the following eligibility criteria will be asked to take part in the study. Inclusion criteria: 1) a current WP smoker for at least the past 6 months, 2) smoke WP ≥ 3 times over the past 6 months, 3) Lebanese Waterpipe Dependence Scale-11 (LWDS-11) score of ≤ 9 (Low Dependence) or ≥ 10 (High Dependence), 4) between 18-50 years old, 5) willing to provide informed consent and 6) abstain from all tobacco, nicotine, and marijuana use for at least 12 hours prior to each of the four sessions. Exclusion criteria: 1) self-reported diagnosis of lung disease including asthma, cystic fibrosis, or chronic obstructive pulmonary disease, 2) history of cardiac event or distress within the past 3 months, 3) currently pregnant, planning to become pregnant, or breastfeeding (will be verified with urine pregnancy test at first session visit), and 4) any use of other illicit drugs during the last 30 days. Note: There are high levels of poly-tobacco use (35-45%) among WP smokers;^{1,18} as such, consistent with previous WP studies, the current eligibility criteria allows some flexibility in the use of other tobacco.

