Power and Data Analytic Plan: Power - Aim 1 (assumes 20% attrition of 82 participants recruited): Overall levels of smoke inhalation is our primary outcome; thus, we will estimate power based on this outcome. As no study to date has investigated the impact of WP flavoring, assumptions are based on a clinical laboratory investigation of percent changes in smokers' topography while smoking menthol vs. non-menthol cigarettes.⁷⁷ According to Chow et al.,⁷⁶ 60 WP users in a Williams 6×4 crossover design achieve >87.5% power to detect a decrease of ≥23L (or ≥20% decrease for unflavored-very low sweetened vs. flavored-sweetened) and ≥18L (unflavored-very low sweetened vs. unflavored-sweetened) in total volume of smoke inhaled using two-sided tests with 0.025 alpha level (used to adjust for the aforementioned 2 pairwise comparisons), conservatively assuming a mean total volume of 115L, 110L, 100L, and 92L for flavored-sweetened, unflavored-sweetened, flavored-very low sweetened, and unflavored-very low sweetened condition, respectively, a common standard deviation of 30L, and a within-subject correlation varying from 0.1 to 0.8. Power - Aim 2: Based on a comparison study of puff topography between high vs. low dependent WP smokers,⁶³ we assume a decrease of 10L (unflavored-very low sweetened vs. flavored-sweetened) and 5L (unflavored-very low sweetened vs. unflavored-sweetened) in total volume of smoke inhaled among high dependence WP users, and a decrease of 44L (or 40% decrease for unflavored-very low sweetened vs. flavored-sweetened) and 39L (unflavored-very low sweetened vs. unflavored-sweetened) in total volume of smoke inhaled among low dependence WP users. As in the power calculation for Aim 1, we assume a common standard deviation of 30L in total volume and a within-subject correlation varying from 0.1 to 0.8. Based on these assumptions, we estimate that 30 high dependence and 30 low dependence WP users achieve >83% power to detect the difference between high and low dependence groups in terms of Δ total volume (unflavored-very low sweetened vs. flavored-sweetened or unflavored-very low sweetened vs. unflavored-sweetened), using a two-sided, two-sample t-test with an adjusted alpha level of 0.025.

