Data Analytic Plan: Data will be summarized using mean (SD). Both overall and stratified (by dependence level) statistics will be reported. For Aim 1, we will use linear mixed effects models (with a random subject effect) to assess the main effect of flavor on total volume of smoke inhaled, abuse liability score, nicotine and CO exposure levels. In addition, period and carryover effects will be considered in the model. All pairwise comparisons for the main effect of flavor will be conducted and Bonferroni-adjusted p-values reported. For Aim 2, we will further include dependence level (high vs. low) and its interaction with flavoring in the linear mixed effects models (as in Aim 1) for outcomes including total volume of smoke inhaled, interest in continued WP use, abuse liability score, and nicotine and CO exposure levels. If the interaction term is significant, flavoring group differences in the outcome for high and low dependence subjects will be compared using contrasts, again adjusting for multiple comparisons with Bonferroni's method. Data will be transformed as appropriate. Missing data will not be imputed and likelihood based linear mixed models will yield valid statistical inference under missing at random (MAR) and ignorable missing mechanism assumptions. A two-sided p-value of <0.05 defines statistical significance. The SAS software (v9.3, Cary, NC) will be used for all data analyses.

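### Aim 1 omits the flavor-by-dependence interaction that the power section predicts, so its total-volume standard errors come out somewhat too large; reading the contrasts from the Aim 2 model corrects this at almost no cost

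*Combined protocol and SAP*

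**What the plan says.** Under Data Analytic Plan, Aim 1 uses a mixed model with a random subject effect "to assess the main effect of flavor on total volume of smoke inhaled", with abuse liability, nicotine and CO analyzed the same way. The only further terms are these: "period and carryover effects will be considered in the model". All pairwise flavor comparisons are to be tested with Bonferroni adjustment.

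Dependence enters one step later: "For Aim 2, we will further include dependence level (high vs. low) and its interaction with flavoring". Total volume is an outcome of that model too. The same section promises descriptive results by group: "Both overall and stratified (by dependence level) statistics will be reported".

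Two other places matter. Participants fixes the group sizes: "A total of 94 current WP smokers (47 low dependent, 47 high dependent) will be recruited", with 76 expected to complete (38 and 38 in Specific Aims). Power - Aim 2 gives the expected effects on total volume by group. In low dependence users it assumes "a decrease of 44L (or 40% decrease for unflavored-very low sweetened vs. flavored-sweetened" and 39 L against unflavored-sweetened. In high dependence users the corresponding drops are 10 L and 5 L.

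**The concern.** Total volume of smoke inhaled is the primary outcome, and the plan itself predicts that the product effect on it differs strongly between two groups whose sizes are set by design. A model that fits one common flavor effect treats this predicted difference as noise. With a single random subject effect and one pooled residual, the noise is spread over all six pairwise total-volume comparisons and enlarges their standard errors and p-values.

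What is at stake is efficiency, not validity. The groups are of equal size, so with complete data the estimated Aim 1 contrasts are the same under either model. Only the reported uncertainty is too large. This matters most for H1a, which claims a full four-step order and so depends on small differences between neighboring products.

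**Working it through.** **Inputs.** From Power - Aim 1: SD 30 L, within-subject correlation (rho) 0.1 to 0.8, 60 participants, two-sided alpha 0.025, and means of 115, 110, 100 and 92 L for flavored-sweetened, unflavored-sweetened, flavored-very low sweetened and unflavored-very low sweetened. From Power - Aim 2: drops of 44 and 39 L (low) against 10 and 5 L (high), with 30 per group.

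**The plan's own figures.**
- Aim 1, 18 L, rho 0.1: variance of a within-subject difference = 2 × 900 × 0.9 = 1620; SE = √(1620/60) = 5.20 L. A paired t-test with 59 df at alpha 0.025 has 87.5% power, as stated.
- Aim 2: 44 − 10 = 34 L and 39 − 5 = 34 L. SE = √1620 × √(2/30) = 10.39 L. The two-sample t-test has 83.1% power, matching the stated figure of more than 83%. This calculation uses 30 L as the SD within a dependence group.

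**Size of the omitted interaction.** Flavored-sweetened minus unflavored-sweetened is 5 L in both groups (10 − 5 and 44 − 39), so these two products carry no interaction between them. Unflavored-very low sweetened carries ±34/2 = ±17 L. For flavored-very low sweetened the documents give no group figures; I assume an extra drop in the low group of 0, 17 or 34 L, that is ±0, ±8.5 or ±17 L.

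Added residual variance = sum of squared deviations of (0, 0, x, 17) from their mean, divided by 3:
- x = 0: 216.75/3 = 72 L²
- x = 8.5: 198.69/3 = 66 L²
- x = 17: 289/3 = 96 L²

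**Effect on the standard errors.** The within-group residual variance is 900(1 − rho). With 76 completers, SE = √(2 × residual variance/76).

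| rho | Residual variance | SE with interaction | SE without | SE widening |
|---|---|---|---|---|
| 0.1 | 810 | 4.62 L | 4.80-4.88 L | 4-6% |
| 0.5 | 450 | 3.44 L | 3.69-3.79 L | 7-10% |
| 0.8 | 180 | 2.18 L | 2.55-2.70 L | 17-24% |

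As a check on the cause, simulated mixed models with 60 participants were refitted with dependence as a main effect only. The SE did not move: 5.43 against 5.42 L at rho 0.1, and 2.92 against 2.92 L at rho 0.8.

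**Effect on power.** Simulation with 38 + 38 completers, the Aim 1 means, and alpha 0.05/6 for the six Bonferroni-adjusted comparisons; power with against without the interaction:
- 23 L: 99.0% against 98.5-98.7% at rho 0.1; about 100% either way at 0.5 and 0.8.
- 18 L: 89% against 86-87% at rho 0.1; 99.5% against 98.9-99.1% at 0.5; about 100% either way at 0.8.
- 10 L (110 vs 100): 60-61% against 48-53% at rho 0.5; 97% against 90-92% at 0.8.
- 8 L (100 vs 92): 36-37% against 27-31% at rho 0.5; 84-85% against 64-71% at 0.8.

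**The case against.** The strongest reply is that little is lost where the plan made a promise. The Power section covers only the 23 L and 18 L contrasts, and these lose at most about 3 points. The steps that lose more were never powered; the 8 L step reaches only 36-37% at rho 0.5 even with the better model. The error is conservative and creates no false positive, and the better model is already specified under Aim 2. All of this stands. It limits the importance of the point but does not remove it, because the Aim 1 comparisons as written are not taken from that model.

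Three further limits also stand. First, the Aim 1 power text gives 30 L for 60 users without division by dependence. If that SD already includes variation due to dependence, the stated Aim 1 power already carries the cost; the documents do not settle this. Second, the group effects average (44 + 10)/2 = 27 L and (39 + 5)/2 = 22 L, whereas Aim 1 assumes 23 L and 18 L. The simulation uses the Aim 1 means with the Aim 2 gap, so it combines inputs that do not fully agree. Third, equal weighting of the groups is a choice of what to estimate, because the 50/50 split is a recruitment quota.

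A reader might infer more than the documents support:
- That leaving out dependence as such costs precision. It does not: dependence is constant within a participant, and the random subject effect absorbs it.
- That every Aim 1 comparison is affected. Group-specific figures exist only for total volume, none for nicotine, CO or abuse liability. Within total volume, flavored-sweetened against unflavored-sweetened widens only through the pooled residual.
- That dropout will shift the Aim 1 estimate. With 33 low and 43 high completers, 27 L would become (33 × 44 + 43 × 10)/76 = 24.8 L, but that split is purely illustrative. The plan expects 20% attrition overall and predicts no difference between groups.

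**Conclusion.** The point holds as a modest loss of efficiency for total volume. The Aim 1 model omits an interaction that the plan itself puts at 34 L, and the pooled residual absorbs it. Standard errors widen by about 4-6%, 7-10% and 17-24% at correlations of 0.1, 0.5 and 0.8. The powered contrasts lose about 0-3 points of power. The 8 L and 10 L steps of the H1a order, which the plan tests but does not power, lose roughly 5-10 and 7-13 points at correlation 0.5, and the 8 L step 13-21 points at 0.8.

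These sizes rest on 30 L as the SD within dependence groups, equal groups of 38 completers, one pooled residual, and an assumed extra drop of 0-34 L for flavored-very low sweetened in low dependence users. The planned Aim 1 tests remain valid; they are conservative. The documents do not support a claim that the primary comparison is underpowered or biased for this reason.

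**What to change.** In Data Analytic Plan, state that the Aim 1 pairwise contrasts are estimated from the model already specified for Aim 2 (flavor, dependence level, flavor × dependence, period and carryover as planned, random subject effect) and averaged with equal weight over the two dependence groups. Adding dependence as a covariate alone would not help; the interaction must be in the model.

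The cost is one sentence and about 4 degrees of freedom: 1 for dependence, between participants, and 3 for the interaction, within participants. With 76 completers and four sessions, the within-subject residual has 304 − 76 − 3 = 225 df before period and carryover terms, so more than 200 remain. No new data are needed, and if the interaction proves absent almost nothing is lost. Equal weighting also keeps the Aim 1 estimate from moving if dropout should differ between the groups.

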WP Smoking Session Procedures: After completing the initial screening over the phone or online, participants will be informed of the study procedures and invited to the lab to complete the four WP smoking sessions. To ensure 12-hr abstinence, upon their arrival at the lab, participants will perform exhaled carbon monoxide testing (eCO<20ppm) and confirm that they have not used any nicotine/tobacco/marijuana products over the last 12 hours. Pregnancy exclusion will also be confirmed with a urine test (n.b.: pregnancy tests will be completed at each visit throughout the study). Along with a member of the study staff, the participant will review informed consent to ensure they understand their rights as a participant. Participants will be randomized and complete study procedures in self-selected dyads. The sessions will be counterbalanced and include: 1) smoking preferred flavored-sweetened WP tobacco 2) smoking unflavored-sweetened WP Tobacco and 3) smoking preferred flavored-very low sweetened WP tobacco and 4) smoking unflavored-very low sweetened WP tobacco. Participants will complete all four study visits in the laboratory. Pre-session abstinence from tobacco for at least 12 hours will be mandatory for all participants. Abstinence will be confirmed via participant self-report and an exhaled carbon monoxide monitor (< 20 ppm) for tobacco use. Participant dyads will first complete a 10-minute puffing session separated by 30-second intervals with the prepared hookah and then smoke *ad libitum* for up to 1 hour. This procedure will be completed for all visits. Participants will also complete a minimum 48-hour washout period between sessions.

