Participants will not be allowed to eat, drink or use their phone during the session. Initially, one piece of charcoal will be lit and placed on top of the foil. Our preliminary studies as well as other WP laboratory trials, indicate that one piece of charcoal will not be sufficient for one WP session; thus, participants will be provided additional pre-weighed pieces to use as they wish. Use of additional charcoal will be recorded. Participants will smoke *ad libitum* and a WP puff topography device will discretely record smoking behavior throughout the session, including puff duration, number of puffs, puff volume, puff flow rate, and time between puffs. Blood samples (15mL per sample) and eCO will be collected immediately pre- and post-waterpipe session and during the 10-minute puffing session (one after each 5-minute puffing period). Self-report measures will be administered as indicated in Table 1.

Protocol Adherence and Quality Control: All research staff will have completed Human Subjects and HIPAA training. Standard operating procedures (SOP) have already been developed for a similar but much smaller version of the proposed study. We will spend the first month of the study refining this SOP. All staff will be trained to ensure adherence to the SOP. As is standard practice for our team's current studies, each visit will have its own checklist of specific measures to be completed and the order in which they are to be administered. To reduce data entry errors, we will use secured computer-based questionnaires for participants to complete. All blood samples collected for biomarker analysis will be given individualized bar codes for each participant. All key on-site personnel will meet face-to-face weekly throughout the entire study. Drs. [name] and [name] too will participate in these meetings on a biweekly basis throughout the study. During these meetings, recruitment, enrollment, data collection, data monitoring results, and concerns will be discussed.

[Baseline and Outcome Measures (see Table 1):]

All breath and blood collections will be administered by a trained research assistant at the OTRC during the four study visits. All self-report measures will be self-administered using a computer-based questionnaire. All measures have been previously used by [name] lab and are reliable and valid.

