
Physiological Measures: Plasma Nicotine was chosen as a biomarker because it is the major known addictive constituent in tobacco smoke,⁷³ and is a key ingredient in WP tobacco. Nicotine content can greatly influence the category of users to which WP smoking will appeal, and also affects the extent and pattern of WP use, thus driving exposures to other constituents in the given product. Less than fifteen mL of blood will be collected just before the onset of smoking, after the first 5-minute and 10-minute puff sampling, and immediately after the smoking session (within 5 minutes of the last puff). Study staff will centrifuge samples and freeze two separate aliquots of plasma immediately at -80C for later analysis of nicotine concentrations; analyses will be completed by VCU’s Tobacco Biomarkers Core. Samples will be analyzed according to standardized methods.⁷⁴ Exhaled Carbon Monoxide (eCO) will be collected immediately before and after the smoking session. CO is a cardiotoxin that is rapidly absorbed into the bloodstream when smoke is inhaled into the lungs. WP users inhale much larger amounts of CO than a cigarette smoker, with some reports of acute CO poisoning requiring hospitalization following WP smoking.⁷⁵

Study Design Considerations & Potential Concerns: Placebo WP Tobacco: We considered adding two placebo conditions (tobacco-free, flavor matched WP herbal product, such as Soex Herbal) to further isolate the effect of flavor from the effect of nicotine; however, a tobacco-free, unflavored (or even tobacco flavored) WP herbal product is not currently available. Even if we were to find the product for sale, we were concerned about the feasibility of completing a five session crossover study within the budget and time period of a R03. If any of these products become available, and the current study indicates a pattern of results that would suggest that flavorings impact the outcomes of interest, then we plan to submit a much larger grant to examine WP tobacco flavorings and nicotine on smoking behavior, toxicant exposure and subjective effects.

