Involvement and Design: Participants' eligibility will be determined over the phone or online using a screener and a pregnancy test will be completed at the initial visit to ensure that the participant is not pregnant. Those who are eligible and willing to participate will be invited to sign informed consent and complete their baseline visit. Enrolled WP smokers will complete four, 2-hr long counterbalanced WP smoking sessions that are preceded by 12 hours of overnight tobacco abstinence, biochemically verified by exhaled carbon monoxide (eCO<20ppm). Sessions will be separated by a standard 48-hour washout period. Participants will first complete a controlled 10-minute puffing session separated by 30-second intervals with the prepared hookah and then smoke ad libitum. The WP puff topography device will discretely record smoking behavior throughout the session, including puff duration, number of puffs, puff volume, and time between puffs. Blood samples (15ml per sample), eCO, and self-report measures of craving and withdrawal will be recorded immediately before and after the smoking session with two blood samples (less than 10mL) collected during the 10-minute puffing session. Self-report measures of abuse liability, as well as interest and willingness to continue to use the WP product just smoked will be assessed within 5 minutes after completing the smoking session.

Sources of Materials

All data collection will follow HIPAA guidelines. Data will be collected directly from the participant by a research assistant. Data will include participant responses to computer-based survey questionnaires and collected blood and breath samples.

Access to Identifiable Information and Data Storage: Only research assistants who have completed training in the ethical conduct of research and the study PI ([name]) will have access to individually identifiable private information about human subjects. All data will be treated as confidential and will never be stored or reported in association with identifying information. In the presence of hard copies of signed informed consent,

IRB NUMBER:

7117

IRB APPROVAL DATE:

12/18/2017

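### The nicotine and CO models (H1c, H2d) name no pre-session term although both markers are measured before every session; precision may be lost, possibly very little

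*Combined protocol and SAP*

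**What the plan says.** The Data Analytic Plan lists the Aim 1 outcomes as "total volume of smoke inhaled, abuse liability score, nicotine and CO exposure levels". The named model terms are flavor and a random subject effect, with period and carryover to be considered. Aim 2 adds dependence level and its interaction with flavor. No pre-session value appears in either model, and the exposure level is not defined.

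Both markers are nevertheless measured before each session. WP Smoking Session Procedures says, along with blood sampling, that "eCO will be collected immediately pre- and post-waterpipe session". Physiological Measures says of nicotine that "Less than fifteen mL of blood will be collected just before the onset of smoking", with further samples "after the first 5-minute and 10-minute puff sampling, and immediately after the smoking session", and of CO that "Exhaled Carbon Monoxide (eCO) will be collected immediately before and after the smoking session".

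Three other statements bear on the point:
- On the abstinence check (WP Smoking Session Procedures): "Abstinence will be confirmed via participant self-report and an exhaled carbon monoxide monitor (< 20 ppm) for tobacco use".
- On other products (Participants): "the current eligibility criteria allows some flexibility in the use of other tobacco".
- On the order of events (section 5.1, Involvement and Design): "Participants will first complete a controlled 10-minute puffing session separated by 30-second intervals", followed by ad libitum smoking.

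**The concern.** H1c and H2d are about exposure from the session just smoked. A post-session plasma nicotine or eCO reading also contains whatever was there before smoking began. The random subject effect absorbs a person's average level, so stable differences between people do no harm. It does not absorb leftover exposure that is higher before one session than before another. Such variation is possible, because abstinence is verified by self-report and an eCO limit rather than by a zero reading, and some use of other tobacco is permitted.

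Only precision on secondary outcomes is at stake. Product order is randomized and counterbalanced, so leaving the term out does not bias the flavor contrasts. These outcomes have no power statement, and all six pairwise contrasts among the four products are Bonferroni-adjusted, so precision already paid for by sampling is worth keeping. The undefined outcome adds to the problem: post-session value and change have different precision when neither is adjusted.

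**Working it through.** **Plan's own figures.** The only stated power is for total smoke volume. At the lowest stated correlation, 0.1, the SD of a within-person difference is 30 × √(2 × 0.9) = 40.2 L.
- Aim 1, 60 users, two-sided alpha 0.025: the standard error is 40.2/√60 = 5.2 L. Power by noncentral t (59 df) is 87.5% for 18 L and 98.2% for 23 L.
- Aim 2, 30 per group, difference 44 − 10 = 34 L: the standard error is 40.2 × √(2/30) = 10.4 L. Power (58 df) is 83.1%.

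Both stated figures reproduce. Smoke volume has no pre-session value, so this point does not touch them. No precision figure is stated for nicotine or CO.

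**Gain from adjustment.** Let r be the correlation, within a person and across sessions, between pre- and post-session values. The documents do not give it, so it is assumed over a range. Relative to a post-session model without the term, the variance of a flavor contrast is about 1 − r², and interval width scales with its square root.

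| r | 0 | 0.1 | 0.2 | 0.3 | 0.4 | 0.5 |
|---|---|---|---|---|---|---|
| Relative variance | 1.00 | 0.99 | 0.96 | 0.91 | 0.84 | 0.75 |
| Interval narrower by | 0% | 0.5% | 2% | 5% | 8% | 13% |

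With the planned 76 completers, r = 0.3 is worth 76/0.91 ≈ 84 unadjusted completers, and r = 0.5 is worth 76/0.75 ≈ 101.

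**CO illustration.** Assume leftover CO carries one-for-one into the post-session reading, so r² = (SDpre/SDpost)², both within person. The SDs are assumptions. The second row spreads one person's sessions evenly over 0–20 ppm, SD 20/√12 = 5.8 ppm, which is generous.

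| Relative variance, by SDpost | 15 ppm | 20 ppm | 30 ppm |
|---|---|---|---|
| SDpre 3 ppm | 1 − 9/225 = 0.96 | 1 − 9/400 = 0.98 | 1 − 9/900 = 0.99 |
| SDpre 5.8 ppm | 1 − 33.3/225 = 0.85 | 1 − 33.3/400 = 0.92 | 1 − 33.3/900 = 0.96 |

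**If the level means change.** With k = SDpre/SDpost, a change score has relative variance 1 + k² − 2rk. Subtracting 1 − r² leaves (k − r)², which is never negative. Adjustment is therefore never less precise, apart from a degree of freedom. Under one-for-one carryover r = k and the advantage is zero.

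**Simulation of the recommended model.** Set-up: 76 subjects, four periods, balanced Williams square (19 per sequence), flavor and period terms, random intercept with known variance components, deviation and subject-mean terms, true contrast 0.30, 6,000 runs per cell. Relative variance at between-session correlation 0.5:

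| r | 0 | 0.1 | 0.2 | 0.3 | 0.4 | 0.5 |
|---|---|---|---|---|---|---|
| Adjusted, complete | 1.01 | 1.00 | 0.96 | 0.91 | 0.85 | 0.75 |
| 10% of pre-values missing, sessions dropped | 1.16 | 1.16 | 1.09 | 1.04 | 0.96 | 0.87 |
| 10% missing, sessions kept (deviation 0) | 1.01 | 1.00 | 0.96 | 0.93 | 0.87 | 0.79 |

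Mean estimates were 0.297–0.305 in every cell, so there is no bias with or without the terms. Over between-session correlations 0.1–0.8 (the range the plan states for smoke volume) and r up to 0.3, dropping sessions gave 1.04–1.16 and keeping them 0.93–1.01. A separate simulation of the same design, 3,000 runs per cell, gave 1.00, 0.91 and 0.76 for the adjusted model at r = 0, 0.3 and 0.5.

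**The case against.** The strongest reply is that no loss has been shown. The deciding quantity, r, is not in the documents. Every session requires 12 hours of abstinence, self-report, an eCO limit and a 48-hour washout, and stable differences in other tobacco use already fall into the subject effect. With a pre-session SD of 3 ppm, the CO intervals narrow by only about 0.5% to 2%. If the investigators meant change from pre-session, the pre-session value is already used and the gain may be nothing. All of this stands, and it limits the point to precision on secondary outcomes. It does not argue against using a value already in hand when the worst simulated cost is about 1% of variance.

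Several smaller objections also stand, without altering the core:
- The simulated ratios are idealized. They use known variance components and independent subjects, while participants attend in self-selected dyads.
- The 10% missing rate is assumed. For eCO it should be lower, since the reading is the entry check at each visit.
- The plan allows transformation of outcomes, so the scale of the covariate needs stating.
- The eCO sentence in WP Smoking Session Procedures can be read as adding readings during the 10-minute puffing period, whereas Physiological Measures has eCO only before and after smoking.

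Preferring the post-session value to change might look arbitrary. It is not a contested choice here: change equals the post-session value minus the deviation and minus the subject mean, so once both terms are in the model the flavor contrasts are identical wherever the pre-session value is observed.

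**Conclusion.** The concern holds. The plan collects a session-specific pre-value for both exposure markers, does not use it in the stated models, and leaves the outcome undefined. Relative to an unadjusted post-session analysis, the cost is 0–4% of contrast variance for r of 0–0.2, 9% at 0.3 and 25% at 0.5. The abstinence rule may put the true figure at the low end, possibly near zero. These sizes rest on assumed correlations and SDs. The change is worth making because it is nearly free; it is not a flaw that threatens the trial's main conclusion. Confidence in its practical size is medium.

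**What to change.** In the Data Analytic Plan:

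1. Define the nicotine and CO outcomes for H1c and H2d as the post-session value. The 5- and 10-minute nicotine samples come from the controlled puffing before ad libitum smoking, while Predicted Results ties exposure to total puff volume, so they may be analysed separately. State whether any eCO is taken during the puffing period.
2. In the Aim 1 and Aim 2 models for these outcomes, add two terms: the same-session pre-value as a deviation from the subject's own mean, and the subject's mean pre-value. State the scale of these terms if the outcome is transformed.
3. Keep a session whose pre-value is missing by setting its deviation to 0, and use the overall mean for the subject-mean term if a subject has no pre-values. Report how many such sessions there are. Reword the sentence that rules out imputation so that it covers outcomes and not this covariate.
4. Dependence groups are not randomized, and Predicted Results expects a difference between them across all sessions. Report that comparison with and without the subject-mean term, naming in advance which is the main one.

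The cost is SAP wording, two model terms per outcome and one covariate rule, with no new data. Item 3 matters: if software silently drops incomplete sessions, adjustment can do worse than none, as the simulation shows for r up to 0.3.
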